## LIST OF ABBREVIATIONS AND ACRONYMS

ACHD	Allegheny County Health Department
AE	Adverse event
AIDS	Acquired Immunodeficiency Syndrome
BV	Bacterial vaginosis
CVL	Cervicovaginal lavage
CT	Chlamydia trachomatis
DAIDS	Division of AIDS
EAE	Expedited adverse event
GC	Neisseria gonorrhoeae
HEC	Hydroxyethylcellulose
HIV	Human Immunodeficiency Virus
HSV-1, HSV-2	Herpes Simplex Virus type 1, type 2
IRB	Institutional Review Board
ITT	Intent-to-treat
N-9	Nonoxynol-9
NIAID	National Institute of Allergy and Infectious Disease
NIH	National Institutes of Health
NRTI	Nucleoside reverse transcriptase inhibitor
PCR	Polymerase chain reaction
PSRT	Protocol Safety Review Team
RSC	Regulatory Support Center
RT	Reverse transcriptase
SOP	Standard operating procedure(s)
STI	Sexually transmitted infection

# A study of the safety and acceptability of a placebo vaginal film: FAME 101

## PROTOCOL SUMMARY

**Short Title:** FAME 101

**Protocol Chair:** [name] MPH

**Protocol Co-chair:** [name]

**Sample Size:** Approximately 64

**Study Population:** HIV-uninfected women, 18 – 45 years old

**Study Sites:** Magee-Womens Hospital of UPMC, Pittsburgh, PA

**Study Design:** A phase I, 4 arm, single site, open label placebo trial with randomization to timing of follow-up

Visit 1	Visit 2	Visit 3	Visit 4
-45 days	Day 0	Day 3,7,10 or 14*	Day 21

\*Randomized to timing of Visit 3

**Study Duration:** Accrual of approximately 64 participants is expected to take 6 months. The expected duration of study participation for each participant will be approximately 5 to 11 weeks. This includes the screening period. After enrollment, the study duration is 3 weeks.

**Study Products:** Vaginal Film  
One dose placebo vaginal film (2" x 2" size)

**Study Regimen:** All participants will receive a single dose of vaginal placebo film that will be self-administered

### Primary Objective:

- To assess the safety of a single dose of a placebo film which is intended for extended release of antiretroviral drugs.

### Primary Endpoint:

- Grade 2 or higher Adverse Events

### **Secondary Objectives:**

- Acceptability
  - To describe the acceptability of the placebo vaginal film and identify qualities associated with higher or lower degrees of acceptability

### **Secondary Endpoint:**

- Acceptability
  - Self-reported assessment of qualities of the experience with the film drawn from existing survey on microboidal films, and general acceptability ratings drawn from market research methodology

### **Exploratory Objectives:**

- **Vaginal Microenvironment**
  - To compare the effects of the placebo film on the vaginal microbiota and glycome pre and post study product use
- **Persistence**
  - To describe the persistence of the film at 3,7,10 and 14 days after insertion

### **Exploratory Endpoints:**

- **Vaginal Microenvironment**
  - Cervicovaginal lavage (CVL)
    - Levels of anti-viral activity
    - Lectin microarray
    - Levels of glycoproteins and mucins
    - Levels of cytokine and innate immunity factors
  - Vaginal
    - Quantitative vaginal cultures and quantitative PCR for selected microbiota
    - Nugent score
- **Persistence**
  - Eudragit ®levels in CVL

## 1 KEY ROLES

### 1.1 Protocol Identification

Protocol Title: A study of the safety and acceptability of a placebo vaginal film:

Short Title: FAME 101

Date: September 20, 2017

## 2 INTRODUCTION

### 2.1 HIV prevention and microbicides

Since 1981, HIV has directly or indirectly resulted in the deaths of 25 million people. Each year millions of people worldwide are newly infected with HIV, most recently 2.7 million people in 2008. Sexual transmission accounts for the majority of new HIV infections worldwide. While most cases of sexual transmission involve both a male partner and a female partner, women are disproportionately impacted by the sexual transmission of HIV. This disproportionate impact arises from a combination of biologic, social, and economic factors. Women at risk face formidable challenges in protecting themselves from HIV infection, including power differentials, gender norms, and economic dependence.

Topical microbicides are agents designed to prevent or at least substantially reduce the acquisition and transmission of HIV when applied to the genital or gastrointestinal mucosa. In addition to preventing HIV infection, topical microbicides may satisfy two critical needs: affordability and female control. Topical microbicides also have the potential for high acceptability for both male and female partners. Acceptability and utility of topical microbicides can be maximized by the development of an array of dosing formulations. For all dosing formulations, safety, stability, and efficacy must be established.

Vaginal films are an attractive dosing option for several reasons. In terms of manufacturing, films are inexpensive, scalable, physically and chemically stable, uniform with regards to product content, and amenable to combinations of active ingredients. In terms of use, films are discreet, portable, and easy to store. Vaginal films can deliver fixed doses of microbical agents with minimal mess and without an applicator. The small volume of vaginal films may also result in less dilution of endogenous antiviral or antibacterial properties of vaginal fluids compared to vaginal gels. In studies of spermicidal film, women have found vaginal films to be acceptable. When Vaginal Contraceptive Film (VCF) was compared to foaming tablets containing nonoxynol-9 (N-9), contraceptive film was preferred in three different countries. Ninety-seven percent of 59 Mexican women, 60 percent of 52 Dominican women, and 86 percent of 51 Kenyan women reported liking contraceptive film. In particular, they cited the following favorable characteristics: ease of use, general feel or comfort, additional lubrication, and lack of side effects. Over eighty percent of Cameroonian sex workers, who participated in a large randomized placebo-controlled trial of N-9 film, reported that they would use the film were it found to be effective against HIV. In Zambian focus groups, placebo vaginal film was preferred over placebo vaginal tablets and soft-gel capsules after each product was used once daily for one week. In a study evaluating the acceptability of placebo microbical film, soft gel capsule and tablet, African women were instructed to use each of the three products once daily for 7 consecutive days. The film and soft-gel capsule were chosen significantly more often than the tablet as the preferred dosage form (39%, 37% and 25%, respectively). In this particular study, film and soft gel were preferred because of faster dissolving time and easier insertion. In other studies, participants found vaginal films to be neater than foaming tablets and gel.

### 2.2 Integrated Preclinical/Clinical Program

The Film Antiretroviral Microbicide Evaluation (FAME) program brings together an interdisciplinary group of research scientists from four academic institutions: University of Pittsburgh, University of Washington, Carnegie Mellon University, New York University and the University of Colorado. The long term goal of the program is to develop and evaluate an extended delivery vaginal film containing an integrase inhibitor which could provide protection from HIV for one week or more following a single application. The first iteration of the FAME IPCP established proof of concept that vaginal films containing the antiretrovirals (ARVs) dapivirine and tenofovir can deliver drug to target tissues as effectively as gel formulations of those same ARVs. The

second iteration, of which this is the first clinical trial, strives to develop an extended release formulation of an integrase inhibitor MK-2048 which will provide coverage for 7 days after each use.

### **2.3 Rationale**

This is a phase I randomized trial assessing the safety of a single vaginal placebo film application. In order to develop a vaginal film which can provide extended release of an ARV, the film polymers and formulation have been altered from the cellulose and polyvinyl alcohol films used to deliver dapivirine and tenofovir in previous trials. Therefore, the proposed study will evaluate the safety and persistence of these film polymers when applied vaginally.

HIV-negative women will be randomized to the timing of the follow up visit prior to administration of the placebo vaginal film and. Women will be randomized to return for a clinical evaluation either three days, seven days, ten days, or fourteen days after study product insertion. In addition to safety, the acceptability of this vaginal film intended for extended release of ARVs will be assessed, as will its impact on the vaginal microenvironment. Cervicovaginal lavage and vaginal fluid (as sampled by absorptive material, such as sponge or wick) will be used to assess the impact of the film on the vaginal microbiota and glycome. The film's impact on cellular immunity and inflammation will also be assessed, and the CVL samples will be assessed for changes to the innate anti-HIV activity.

The film is intended to provide HIV protection for a week after a single application. Understanding how long the film remains in the vagina will be an integral part of this study. [name] lab has developed an assay to detect the polymer Eudragit® in cervical vaginal fluid. Genital samples from Visit 1, Visit 3 and Visit 4 will be evaluated for the presence of Eudragit.®. Eudragit was chosen over the other polymers because of technical feasibility for the assay. The other polymers in the film are cellulose based, and it would be very difficult to differentiate between the polymers in a biologic sample. Eudragit, on the other hand has a unique structure. Of note, all of the visible film will be removed with the CVL performed at Visit 3; therefore, no Eudragit® should be detectable at Visit 4.

This study has been designed to add to our knowledge about film application challenges. Product misplacement was noted in the three clinical trials of vaginal film previously conducted at the University of Pittsburgh. While most participants could successfully insert the vaginal films, incorrect film placement was noted for some. In some instances, the vaginal film stuck to the finger after attempted insertion and in other instances the film was visualized on the external genitalia. Because the primary objective of this study is to assess safety and persistence, administration error will be noted immediately after the participant attempts to insert the film. If most the film is noted to be external to the vaginal introitus, the film will be removed by the clinician and a new vaginal film will be placed inside the vagina by the clinician. This will ensure the integrity of the primary objective.

### **2.4 Safety Data: Placebo Film**

The placebo film consists of ingredients with a proven safety record. Table 1 outlines documented usage with film excipients per the FDA database for inactive ingredients in approved drug products.

**Table 1: Placebo Film Excipients**

Excipient	Use	Concentration*	History of Vaginal Use
Hydroxypropyl methyl cellulose (HPMC) or Hypromellose**, USP	Film Forming Polymer	Vaginal; gel 3.5% Vaginal; tablet 5 mg Rectal; gel 4.35% (listed as hypromelloses**)	ESTRACE® Cream and VAGIFEM® vaginal tablets, tenofovir and dapivirine vaginal films
Propylene glycol (PG), USP	Plasticizer/Dispersant	Vaginal; emulsion, cream 20% Vaginal; gel 3% Vaginal; suppository 252 mg	VCF dissolving vaginal lubricant film (5%) 
Hydroxyethyl cellulose, NF	Film Forming Polymer	Buccal ; film 54.92 mg Oral; tablet, extended release 400mg Topical; gel 1.75%w/w	Tenofovir vaginal film, tenofovir and dapivirine vaginal gels
Polyethylene glycol 400, NF	Plasticizer/Dispersant	Rectal; suppository 24.8% Topical; cream 1.5%w/w Topical; cream, emulsion, sustained release 7.5%w/w	Vaginal suppository
Ammonio Methacrylate Copolymer Type B (Eudragit®), NF	Extended Release Polymer	Oral; capsule, extended release 35.7mg Oral;tablet, extended release 11.05mg Tablet, film coated 8mg	*
Hydroxypropyl cellulose, NF	Film Forming Polymer	Buccal; film 100.04mg Topical; patch Transdermal; film controlled release 19mg Oral; tablet (immed./comp. Release), film coated 24mg	*

\*Although there is not a history of vaginal use, these excipients have been used extensively in other pharmaceutical products such as buccal films, oral tablets, and in transdermal and topical films and patches.

Safety evaluation of the extended release placebo film was performed in a nonhuman primate model. Six pigtailed macaques were exposed to two films per week for two weeks, which is double the proposed human dosing (intended dosing is one film per week). In total, four films were delivered to each macaque over fourteen days. The vaginal microbiota, vaginal pH, and number of PMNs on gram stained vaginal smears were assessed before the first film placement and after the fourth film placement. The integrity of the cervicovaginal tissues was assessed by colposcopy at each film placement. Of note, there was visible film in the vagina with each film placement. No adverse events were noted by colposcopy; microbiota remained stable with no effect noted on the beneficial H2O2 producing microorganisms; vaginal pH remained within normal range; and PMN counts remained within the normal range even after more frequent administration than intended for use ([name], personal communication). The entire study report is presented in Appendix IV.

Though the films used had different excipients, the tenofovir and dapivirine vaginal films used in FAME-02 and FAME-04 were found to be safe with no Grade 3 or higher Adverse Events attributed to study product and no changes in the vaginal microenvironment noted. The macaque exposure model utilized for this protocol provided the initial assurances of safety for those studies as well.

## **2.5 Summary**

It is appropriate to advance this placebo film into a clinical trial for safety for the following reasons:

- The individual ingredients used in the film have a history of safe use in mucosal compartments (gastrointestinal and/or vaginal).
- The same film was found to be safe in macaques without evidence of epithelial disruption despite twice weekly dosing, twice the frequency of intended human use.

## **3 OBJECTIVES**

### **3.1 Primary Objectives**

- To assess the safety of a single dose of a placebo film which is intended for extended release of antiretroviral drugs

### **3.2 Secondary Objectives**

- **Acceptability**

To describe the acceptability of the placebo vaginal film and how different qualities are associated with higher or lower degrees of acceptability

### **3.3 Exploratory Objectives**

- **Vaginal Microenvironment**

- To compare the effects of the placebo film on the vaginal microbiota and glycome pre and post study product use.

- **Persistence**

- To describe the persistence of the placebo vaginal film at 3, 7, 10 and 14 days after insertion

## **4 STUDY DESIGN**

### **4.1 Identification of Study Design**

This is, single site, open label placebo trial with randomized timing of follow-up

### **4.2 Summary of Major Endpoints**

Grade 2 or higher Adverse Events deemed related to study product

### **4.3 Description of Study Population**

The study population will be HIV-uninfected women who meet criteria outlined in Section 5.

### **4.4 Time to Complete Accrual**

Accrual is expected to be completed in approximately 6 months.

## **4.5 Study Groups**

All participants will receive a single dose of the vaginal film. They will be randomized at enrollment to the timing of Visit 3. In total, there will be four groups:

- Visit 3 at Day 3 (range days 2-4)
- Visit 3 at Day 7 (range days 6-8)
- Visit 3 at Day 10 (range days 9-11)
- Visit 3 at Day 14 (range days 12-16)

## **4.6 Expected Duration of Participation**

The duration of study participation per woman is expected to be approximately 5-11 weeks. This includes the screening period.

## **4.7 Site**

There is a single study site: Magee-Womens Hospital, Pittsburgh, PA.

# **5 STUDY POPULATION**

## **5.1 Selection of the Study Population**

The inclusion and exclusion criteria in this section will be utilized to ensure the appropriate selection of study participants.

## **5.2 Recruitment**

Participants will be recruited from a variety of sources including the ambulatory clinic of Magee-Womens Hospital and the surrounding population. Participants will also be referred to the study from other local research projects and other health and social service providers serving the target study population. Recruitment materials will be approved by the University of Pittsburgh Institutional Review Board.

## **5.3 Retention**

Once a participant is enrolled, the study site will make every effort to retain her in follow-up to minimize possible bias associated with loss-to-follow-up. The site will implement the following procedures to enhance retention:

- Thorough explanation of the study visit schedule and procedural requirements during the informed consent process and re-emphasis at each study visit.
- Thorough explanation of the importance of all 4 study groups to the overall success of the study.
- Collection of detailed locator information at the study screening visits, and active review and updating of this information at each subsequent visit.
- Use of appropriate and timely visit reminder mechanisms.
- Immediate follow-up on missed visits.

Study sites will use a participant tracking mechanism to facilitate visit scheduling and timely identification and follow-up on missed visits.

## **5.4 Inclusion Criteria**

Women must meet all the following criteria to be eligible for inclusion in the study:

- 1) Age 18 through 45 years (inclusive) at screening
- 2) Able and willing to provide written informed consent to be screened for and to take part in the study.

- 3) Able and willing to provide adequate locator information
- 4) HIV-uninfected based on testing performed by study staff at screening (per algorithm in Appendix II)
- 5) In general good health as determined by the site clinician
- 6) Agree to be sexually abstinent for 48 hours prior to each visit and from Visit 2 to seven days after Visit 3
- 7) At screening, agrees to abstain from any other intravaginal product or penetration (including sex toys, excluding tampons) for 48 hours prior to each visit and between Visit 2 and 3.
- 8) Willingness to undergo all study-related assessments and follow all study-related procedures
- 9) At screening and enrollment, agrees not to participate in other research studies involving drugs, medical devices, or vaginal products while enrolled in this trial

## **5.5 Exclusion Criteria**

Women who meet any of the following criteria by participant report will be excluded from the study. Of note, the study is limited to premenopausal women with an intact uterus because the mucosal immune environment differs substantially between pre- and post- menopausal women. Therefore, inclusion of post-menopausal women would introduce heterogeneity into the population.

- 1.) Menopause (as defined as amenorrhea for one year or more without an alternative etiology)
- 2.) Hysterectomy
- 3.) Participant report of any of the following:
  - a) Known adverse reaction to any of the study products (ever)
  - b) Known adverse reaction to latex (ever)
  - c) Non- therapeutic injection drug use in the 12 months prior to Screening
  - d) Surgical procedure involving the pelvis in the 90 days prior to enrollment (includes dilation and curettage or evacuation, and cryosurgery; does not include cervical biopsy for evaluation of an abnormal pap smear)
  - e) Participation in a drug, spermicide and/or microbicide study in the 30 days prior to enrollment or anticipated participation in an investigational drug study until completion of the study
  - f) Currently pregnant or pregnancy within 42 days prior to enrollment
  - g) Currently lactating
  - h) Use of a diaphragm, NuvaRing®, or spermicide for contraception
  - i) Internal vaginal use of any device or product (except tampons) in the 48 hours prior to enrollment
- 4.) Urogenital infection or suspected infection within 14 days of enrollment including: symptomatic candidiasis, trichomonas vaginalis, and symptomatic bacterial vaginosis; or cervical infection, including *N. gonorrhoeae* (GC), *C. trachomatis* (CT), or mucopurulent cervicitis; syphilis; HSV lesions, or other sores (Note: seropositive HSV without active lesions will not be excluded); acute pelvic inflammatory disease; urinary tract infection; recent exposure to a partner with GC, CT, Trichomonas, syphilis, or NGU

- 5.) Antibiotic or antifungal therapy (vaginal or systemic) within 14 days of enrollment
- 6.) As determined by the PI, has any significant uncontrolled active or chronic cardiovascular, renal, liver, hematologic, neurologic, gastrointestinal, psychiatric, endocrine, respiratory, immunologic disorder or infectious disease
- 7.) Menses-like bleeding at the time of the Enrollment visit\* or expected menses-like bleeding within 14 days of the Enrollment visit  
(\*Women who have vaginal bleeding at the scheduled Enrollment Visit may return at a different date to be re-examined and possibly enrolled provided they are still within the screening window and meet all criteria.)
- 8.) Any condition that, in the opinion of the Investigator, would preclude provision of consent, make participation in the study unsafe, complicate interpretation of study outcome data, or otherwise interfere with achieving the study objectives

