### 7.3 Visit 2: Enrollment

Subjects who meet the inclusion and exclusion criteria following the Screening Visit may schedule an Enrollment Visit. Care will be taken to schedule the Enrollment visit at a time when the participant is not expecting to be actively bleeding or anticipating her menses within 14 days.

Before performing any enrollment procedures, study staff will confirm eligibility. The participant will undergo a pelvic examination. Pelvic specimens as described below will be collected and the study staff will assess for bleeding. If no bleeding or other exclusionary findings are evident, the participant will then be randomized to the timing of Visit 3. The act of randomization is considered the act of enrollment for this study. Subjects with menses like vaginal bleeding at the Enrollment visit will not be randomized/enrolled at that time. These subjects may be rescheduled if vaginal bleeding resolves before 45 days from Screening have elapsed. If vaginal

bleeding does not resolve during the window period, and the subject expresses interest in enrollment for the study, she may be offered a rescreening attempt.

After eligibility is confirmed, the clinician will go to the Pharmacy to obtain the study product. Participants will be counselled thoroughly on product administration and then handed the film in its packaging. The participant will attempt to insert the film while a site staff member stands behind a curtain to maintain privacy. Should the participant have any concerns or questions, the site staff member will be readily available. Immediately after the participant attempts insertion, the site clinician will do a quick inspection of the external genitalia to assess for proper placement. If the majority of the film is visible outside of the vaginal introitus, the clinician will return to the pharmacy to retrieve a second dose of the vaginal film. The clinician will then remove visible film, insert a speculum, remove visible film from inside the vagina, and place a second film in the proximal third of the vagina using a forceps instrument. After film placement, participants will be scheduled for Visit 3. When Visit 3 occurs will be determined by randomization (3, 7, 10 or 14 days).

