## 7.4 Visit 3: Follow-Up Visit

The timing of Visit 3 will be determined through the randomization process. All participants will be randomized to return either 3,7,10, or 14 days after film insertion. Visit 3 procedures are outlined in Table 4. The windows around these study visits are as follows:

Day 3 (days 2-4)

Day 7 (days 6-8)

Day 10 (days 9-11)

Day 14 (days 12-16)

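### The expected-menses exclusion stops at day 14 but the Day-14 arm's Visit 3 window runs to day 16, so expected menses can meet an evaluable Visit 3 in that arm only

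*Combined protocol and SAP*

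**What the plan says.** Section 5.5, exclusion 7, bars women with "expected menses-like bleeding within 14 days of the Enrollment visit". Section 7.3 has staff book Enrollment when the participant is "not expecting to be actively bleeding or anticipating her menses within 14 days". Both horizons are 14 days from Day 0.

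Section 4.5 sets the Visit 3 windows: "Visit 3 at Day 3 (range days 2-4", "Visit 3 at Day 7 (range days 6-8", "Visit 3 at Day 10 (range days 9-11" and "Visit 3 at Day 14 (range days 12-16". Section 7.4 repeats them.

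Section 9.6.4 makes a participant evaluable if she completes Screening and Enrollment and attends Visit 3 in window. Bleeding plays no part in that definition. Section 7.4 has no rule for a woman who is bleeding at Visit 3.

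Two provisions bear on the point. Section 9.1 says that menstrual symptoms are collected by symptom review. Section 9.6.3 ends by naming time since last menstrual period as a potential confounder, without saying at which visit it is measured.

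**The concern.** Reading "expected menses-like bleeding within 14 days of the Enrollment visit" as covering days 0 to 14, the earliest expected onset in an eligible woman is day 15. The Day-3, Day-7 and Day-10 windows close before then. The Day-14 window does not: days 15 and 16, two of its five days, lie beyond the horizon. Expected menses at Visit 3 is thus possible in one arm and not in the other three.

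Randomizing the timing of Visit 3 should make the arms comparable apart from time since insertion. Bleeding at Visit 3 that is concentrated in the longest arm can look like a late effect of the film. The macaque report in Appendix IV shows that menses changes vaginal samples. Three of the four samples with pH 7.0 or higher were taken during menses. On Day 0, before any film, the two menstruating animals had mean PMN counts of 11 and 26.8, against 0 to 1 in the other five. Section 9.6.3 compares cytokines, mucins, antiviral activity and flora between arms and against days of exposure. Visit 3 is also the only informative persistence sample, because Section 2.3 says that visible film is removed then.

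**Working it through.** The plan gives no figure for bleeding at Visit 3, so there is none to reproduce. The power statement in Section 9.2 plays no part here.

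**Window against horizon (from the documents).** Window days after day 14: Day-3 arm 0 of 3, Day-7 arm 0 of 3, Day-10 arm 0 of 3, Day-14 arm 2 of 5. One woman is 1/16 = 6.25 points of an arm percentage.

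**Assumptions (not in the documents).** 28-day cycle; 5-day bleed; expected onset t equally likely on each eligible day; visits spread evenly over the window unless stated. The earliest t is 15. The latest is 28 − 5 = 23, since a later t would mean that the previous bleed is still present at Enrollment. That gives 9 values.

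**Menses exactly as predicted.** A visit on day v meets menses if t ≤ v ≤ t + 4.
- Days 12, 13 and 14: 0 of 9. Day 15: 1/9 (t = 15). Day 16: 2/9 (t = 15 or 16).
- Even spread over days 12-16: (0 + 0 + 0 + 1/9 + 2/9)/5 = 1/15 = 6.7%, and 16 × 0.067 = 1.1 women.
- Weights 1:2:3:2:1 around day 14: (2 × 1/9 + 1 × 2/9)/9 = 4/81 = 4.9%, or 0.8 woman.
- All visits on day 14: 0%. All on day 16: 2/9 = 22%, or 3.6 women.

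**Error in the predicted date.** Let actual onset be t plus a normal error with standard deviation SD, rounded to a whole day. Then P(bleeding at v given t) = Φ((v + 0.5 − t)/SD) − Φ((v − 4.5 − t)/SD), averaged over t and over the window days. Results in percent:

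| SD (days) | Day-10 arm, as planned | Day-14 arm, as planned | Day-14 arm, horizon 16 days | Day-14 arm, window 12-14 |
|---|---|---|---|---|
| 0 | 0.0 | 6.7 | 0.0 | 0.0 |
| 1 | 0.0 | 7.9 | 1.3 | 1.7 |
| 2 | 0.3 | 10.7 | 4.0 | 4.9 |
| 3 | 1.6 | 13.6 | 7.6 | 8.5 |
| 4 | 3.7 | 15.8 | 10.9 | 11.5 |

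The gap's share is the planned figure minus the figure with a 16-day horizon: 6.7, 6.6, 6.7, 6.0 and 4.9 points for SD 0 to 4. For SD 0 to 3 that is about 1 woman in 16 (16 × 0.060 = 0.96; 16 × 0.067 = 1.07). What remains (1.3, 4.0, 7.6 and 10.9 points for SD 1 to 4) is menses arriving early, which the gap does not cause.

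If every visit fell on day 14 with SD 2, bleeding would be 8.7%, all of it early onset. A 16-day horizon would lower that to 2.3%, but by adding a margin against early onset, not by closing the gap.

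**Side effects of a 16-day horizon.** Eligible enrollment days per cycle are cycle length − 5 − horizon: 28 days, 9 to 7; 24 days, 5 to 3; 21 days, 2 to 0. Menses at Visit 4 (days 18-25) rises in every arm from about 50% to 55% with exact prediction, and from about 45% to 49% with SD 2.

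**The case against.** The case for leaving the plan alone has several parts.

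- **Day 14 is the target.** Section 10.3 ties the Visit 3 payment to keeping the date, and staff book Visit 3 knowing when menses is expected, so they can use days 12-14. This stands as a reason to expect less than the even-spread figure. But no section tells staff to do so, and days 15 and 16 count as compliant.
- **The plan adjusts for menstrual timing.** Time since last menstrual period could identify a woman bleeding at Visit 3, if measured then. It can enter the mixed and GEE regressions. It cannot enter the ANOVA, Kruskal-Wallis, Fisher, Mann-Whitney or McNemar tests, or the persistence percentages in Table 7. The mitigation is real but partial.
- **Only exploratory endpoints are touched.** This stands. Section 3.3 makes both microenvironment and persistence exploratory.
- **The inputs are assumed.** This stands. Among hormonal methods only the vaginal ring is named as an exclusion, so women without regular menses may enroll and would lower every figure.

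A reader might also infer that the criterion was meant to cover the whole window. The documents do not state its purpose, and matching the nominal day is a defensible choice. A reader might infer that menses carries film out and would mimic faster loss. The documents do not show this. Appendix IV records residual film in menstruating macaques, although films were replaced every three to four days, so it does not rule out washout either.

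**Conclusion.** The mismatch is in the text and needs no assumption: the menses screen ends at day 14, one arm's Visit 3 window ends at day 16, and nothing covers bleeding at that visit.

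Its size is modest and rests on the assumed cycle, bleed length and visit spread: about 6 to 7 points, or about 1 of 16 women, for prediction error up to 3 days. A reader might charge the whole 8% to 14% (SD 1 to 3) to the criterion, but the rest is early onset. The 22% figure requires every visit to fall on day 16.

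The consequence is possible confounding of the exploratory Day-14 microenvironment contrasts. The persistence estimate may be affected too, but that depends on an effect of menses on film that the documents do not establish. Nothing here shows an effect on the primary adverse event proportion or the sample size. Menses at Visit 4 can occur in all arms and is not part of this point. The change is worth making because it is cheap and the unadjusted comparisons cannot correct for the imbalance.

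**What to change.** Reconcile the horizon in Sections 5.5 and 7.3 with the Day-14 window in Sections 4.5 and 7.4, so that both end on the same day. The sponsor can do this in either of two ways:

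- Extend the horizon to the end of the window, for all women before randomization. This costs 2 of 9 eligible days in a 28-day cycle, more in proportion for short cycles, and slightly raises menses at Visit 4 in every arm.
- End the Day-14 window at the horizon. This keeps eligibility as it is but removes tolerance for late visits, so some women would become non-evaluable and need replacing.

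With either option, record bleeding (yes or no) at Visit 3 and state at which visit time since last menstrual period is measured. Add to Section 9.6.3 a repeat of the Visit 3 exploratory comparisons, including persistence, without samples taken during bleeding. Early onset will still produce some bleeding in the Day-14 arm, which this sensitivity analysis addresses. Its cost is one data item and one extra set of tables.
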